9.4. Variables

Outcome events will be the pre-specified potential safety concerns, including those that were part of Paxlovid or identified after the EUA post marketing. The list of events of interest is provided below. This list of outcome events was chosen based on clinician's expert opinion, biologic plausibility, and feasibility of identification in EHR or claims data. Other potential safety concerns that arise during the post marketing, clinical trials, or based on emerging literature related to Paxlovid safety will be included in subsequent refreshes of the cohorts, or as rapid queries in response to regulatory authority requests.

Potential Safety Outcomes of Interests*

- 1. Renal impairment.
- Hepatic impairment.
- 3. Other potential safety events of interest (eg, Diarrhea, Dysgeusia, Hypersensitivity reaction/allergic reactions, and other additional potential safety events of interest may be added over time).

* The potential safety outcomes of interests listed above can be further evaluated by the covariates including (demongraphics, drug-drug interactions etc.).

Potential effectiveness of interests*

- Hospitalization;
- All-cause mortality;
- ICU/Mechanical Vitalization;
- In Hospital death.

COVID-19 complications/interventions (within 30 days of COVID 19 diagnosis):

- Pneumonia;
- Kidney failure;
- Thrombotic event;
- Acute respiratory distress syndrome (ARDS);
- HF;
- Sepsis/septic shock;
- Hospitalization;
- All-cause mortality;
- In hospital death;
- Multi-organ dysfunction/failure;
- Mechanical ventilation/ECMO (Extracorporeal membrane oxygenation).
- Vasopressor use

Time to clinical events:

- Time from index date (Section 9.2.2.3) to admission;
- Time from index date (Section 9.2.2.3) to the events above.

^{*}The outcomes may be removed to added depending on the data availability for proper analyses.

COVID-19 long term health effects:

Headache;

The following conditions may be considered for COVID-19 long term effects. This is not an exclusive list. Specific definition and follow up windows of long COVID (eg, greater than 4 weeks, 12 weeks, or 6 months after a COVID diagnosis)⁹⁻¹⁰ will be further defined in SAP.

4 weeks, 12 weeks, or 6 months after a COVID diagnosis) ⁹⁻¹⁰ will be further defined in SAP.
Abdominal pain;
Acute kidney injury;
Alopecia;
Body aches;
• Chest pain;
Cognitive impairment;
• Confusion/delirium;
Nasal congestion;
• Cough;
Anxiety disorders;
• Depressive disorder (includes major depressive disorder, dysthymic disorder);
Post-traumatic stress disorder;
Substance use disorders;
Suicidal behavior and suicide ideation;
• Diarrhea;
Nausea;
 Palpitations or fast-beating or pounding heart;
• Fatigue;
• Hair loss;

Version 3.0, Amendment 2, 23 August 2022

- Intermittent fever;
- Arthralgia or joint pain;
- Anosmia or loss of smell;
- Ageusia or loss of taste;
- Lung function abnormalities;
- Myalgia or muscle pain;
- Myocarditis;
- Pericarditis;
- Post-COVID syndrome (ie, PASC defined by international classification of disease -10-CM (ICD-10-CM) code U09.9);
- Rash;
- Dyspnea or shortness of breath;
- Insomnia;
- Others to be added.

COVID-19 Re-infection:

Re-infection of COVID-19 within certain time windows after previous COVID 19 infection or rebound with COVID-19 infection within certain time window post Paxlovid prescription date (as needed). This will be further defined in SAP.

9.5. Covariates

Covariates will include baseline demographic, clinical characteristics, medications, and health utilization, as well as those needed for the study cohort inclusion and exclusion criteria. These are not intended to be the exclusive lists. Adjustments of the covariates may be made and additional variables may be added in SAP as needed over time. The code lists of conditions and medications (if applicable) will be provided in SAP.

Demographics:

- Age;
- Gender;

- Race;
- Ethnicity;
- Region;
- Insurance.

Clinical Characteristics:

- Asthma;
- Autoimmune diseases.
 - Multiple Sclerosis; Sjogren's syndrome; Guillain-Barre; idiopathic thrombocytopenia purpura; autoimmune thyroiditis; giant cell arteritis; psoriasis; systemic or cutaneous lupus erythematosus; autoimmune arthritis/rheumatoid arthritis, glomerulonephritis.
- BMI.
- Cancer.
- Cerebrovascular disease or stroke (including transient ischemic attack).
- CKD.
- COPD.
- ILD.
- Coronary heart disease.
- Cardiomyopathies.
- Deyo-Charlson Comorbidity Index Score.
- Hepatitis B virus (HBV), HCV, HIV infection.
- Hyperlipidemia.
- Hypertension.
- Liver disease.
- Sickle cell disease.

- Smoking.
- Diabetes mellitus.
- Pregnancy status.
- C-Reactive Protein (CRP; within 10 days prior to the index date).
- Lactate dehydrogenase (LDH; within 10 days prior to the index date).
- Ferritin (within 10 days prior to the index date).
- D-dimer (within 10 days prior to the index date).
- Note: A focus of these lab tests would be for inpatients.

Medications that are contraindicated with Paxlovid (FDA EUA label):

- Alpha1-adrenoreceptor antagonist: alfuzosin;
- Analgesics: pethidine, propoxyphene;
- Antianginal: ranolazine;
- Antiarrhythmic: amiodarone, dronedarone, flecainide, propafenone, quinidine;
- Anti-gout: colchicine;
- Antipsychotics: lurasidone, pimozide, clozapine;
- Ergot derivatives: dihydroergotamine, ergotamine, methylergonovine;
- 3-hydroxy-3-methylglutaryl co-enzyme A (HMG-CoA) reductase inhibitors: lovastatin, simvastatin;
- PDE5 inhibitor: sildenafil (Revatio®) when used for pulmonary arterial hypertension (PAH);
- Sedative/hypnotics: triazolam, oral midazolam;
- Anticancer drugs: apalutamide;
- Anticonvulsant: carbamazepine, phenobarbital, phenytoin;
- Antimycobacterials: rifampin;

• Herbal products: St. John's Wort (hypericum perforatum).

Medications for treatment of COVID-19/Vaccination for COVID-1:911

Anti-SARS-CoV-2 Antibody Products			
Bamlanivimab/Etesevimab			
Casirivimab/Imdevimab			
Sotrovimab			
Tixagevimab/Cilgavimab			
Bebtelovimab			
Convalescent plasma			
Antiviral therapy			
Remdesivir			
Molnupiravir			
Chloroquine /hydroxychloroquine			
Azithromycin			
Lopinavir/ritonavir			
Ivermectin			
Nitazoxanide			
Ribavirin			
Inteferon-beta			
Immunomodulators			
Systemic Corticosteroids			
Dexamethasone			
Methylprednisolone			
Fluvoxamine			
Interleukin inhibitors			
Tocilizumab			
Sarilumab			
Antithrombotic Therapy			
Heparin			
Covid-19 vaccines			

Health Utilization:

- Emergency room (ER) visit;
- Office visits;
- Telemedicine visits;
- Urgent care visits;
- Number of hospitalizations;

Length of hospital stay.

Paxlovid User Characteristics (in addition to Clinical Characteristics, Medications in "Covariates" in the Section 9.5).

- Demographics.
 - Age. Gender.
 - Race.
 - Ethnicity.
 - Region.
 - Insurance.
 - Comorbidities.
 - Renal impairment.
 - Hepatic impairment.
 - Top 50 Comorbidities in the database.
 - Medications.
 - Top 50 prescriptions in the database.
 - Paxlovid use.
 - Days since index date (Paxlovid prescribed date).
 - Provider.
 - Health Utilization:
 - ER visit.
 - Office visits.
 - Telemedicine visits.
 - Urgent care visits

- Number of hospitalizations
- Length of hospital stay

9.6. Data Sources

Given the urgent need to clinically understand the novel virus of COVID-19, Optum developed a low latency data pipeline that enables minimal data lag, while preserving as much clinical data as possible. The data are sourced from Optum's longitudinal electronic health record (EHR) repository, which is derived from dozens of healthcare provider organizations in the US, including more than 700 hospitals and 7,000 clinics. The data are certified as deidentified by an independent statistical expert following the Health Insurance Portability and Accountability Act (HIPAA) of 1996 statistical deidentification rules and managed according to Optum® customer data use agreements. The COVID-19 dataset incorporates a wide swathe of raw clinical data, including new, unmapped COVID19-specific clinical data points from both inpatient and ambulatory electronic medical records, practice management systems, and numerous other internal systems. Information is processed from across the continuum of care, including acute inpatient stays and outpatient visits. The COVID-19 data capture point-of-care diagnostics specific to the COVID-19 patient during initial presentation, acute illness, and convalescence, with over 500 mapped labs and bedside observations, including COVID-19-specific testing.

The Optum COVID-19 EHR dataset elements included patient-level information: demographics, mortality (captured from Social Security Administration Death Master File, electronic medical records and Centers for Medicare and Medicaid Services), as well as clinical interventions, such as medications prescribed and administered, laboratory results, and vital signs and other biometric measures. The data are comprised of multiple tables that can be linked by a common patient identifier (an anonymous, randomized string of characters). The COVID-19 patient data included patients in the EHR database who had documented clinical care from January 2007 through to the most current monthly data release with a documented exposure to, or had been tested for, SARS-CoV-2 (positive or negative result), and/or had a diagnosis of COVID-19, or acute respiratory illness, after February 1, 2020. Thus, not all patients within the Optum® COVID-19 EHR dataset had received a diagnosis of COVID-19. Patients with COVID-19 were identified via a diagnosis code for SARS-CoV-2, a positive test for SARS-CoV-2 active infection (antigen and/or polymerase chain reaction), and/or a positive antibody test. The Optum® COVID-19 EHR dataset included medical records from 2007, allowing for the utilization of patients' medical history in the analysis.

As we are entering new era of COVID 19 toward end of 2022, monthly delivery of OPTUM COVID EHR 19 will be replaced by OPTUM EHR data with longer latency. Additionally, supplemental OPTUM Claims with likely larger size of Paxlovid patients may be used in additional analyses of Paxlovid (if needed) in this study.

9.7. Study Size

This is a descriptive study with no minimum sample size. This study will be updated with new data annually (or as needed) and made readily accessible to address research questions. All eligible patients during the relevant study periods will be included. If there is a need to add on post-hoc comparative studies analyses, which are not part of the scope of this current study, the feasibility of robust comparisons given accrued sample size will be assessed as described in the SAP.

9.8. Data Management

All study data exist as structured data by the time of study. Analyses will be conducted using SAS (version 9.4 or later, SAS Institute, Cary, NC, USA). As the database will be regularly updated, date and version of the database will be specified in the report of the study, and the intermediate datasets will be archived if the report will be submitted to a regulatory agency or will be published.

The study will be conducted by Quantitative Epidemiology and Analytic Team, Global Medical Epidemiology, Pfizer. The analytic datasets and programs will be stored according to Pfizer's procedures.

9.9. Data Analysis

Baseline characteristics will be summarized for Source Cohort, Trial Similar Subcohorts, and Paxlovid cohort. Means with standard deviations, medians with interquartile will be provided for continuous variables. Numbers and percentages will be provided for dichotomous variables or categorical variables.

For dichotomous endpoints such as COVID-19 complications and outcomes, the crude cumulative incidence and incidence rate of each endpoint will be estimated for the Source Cohort and the Trial Similar Subcohorts. For incidence calculation, only the first of each event occurring in the risk window will be included in the numerator. How to handle prevalence cases prior to the index date for incidence calculation will be further described in SAP depending on the nature of outcomes (eg, acute vs. chronic evets). Cumulative incidence and its 95% confidence interval (CI) will be estimated and illustrated using 1-Kaplan-Meier curves. Incidence rate will be calculated as the number of patients who experience the event divided by the total person time at risk, along with the 95% CI. The follow-up will start on the index date and will end on the first occurrence of an endpoint, disenrollment, study end date, or death, whichever comes first. Different endpoints will not censor each other's follow-up. Subpopulation analyses, as needed, will be detailed in SAP that may include those immunocompromised patients, pediatric population, severe renal patients, Paxlovid users with contraindication medications, patients with multiple infections of COVID 19, or patients received COVID 19 vaccines etc.

For exploratory analysis, machine learning models (eg, LASSO Cox regression, Random Survival Forest (RSF), and XGBoosting (XGB) models) will be used to identify important predictors associated with progression to COVID-19 severe outcomes/manifestations as well as long COIVD. An ensemble method will be used to rank predictors across models and find the strongest predictors for each outcome. Patient-level prediction for the risk of developing severe outcomes/manifestation and long COVID will be performed using the top ensemble predictors. C-index and dynamic AUCs will be used to evaluate model performance. To assess the feasibility of real-world effectiveness of Paxlovid, we will apply propensity score matching (PSM) method to control confounding and PTDM to handle immortal bias. To better understand the impact of incidental hospitalization on the same date of COVID 19 diagnosis date or Paxlovid prescription date, medical note review of patients with the same date hospitalization will be conducted by OPTUM. The structured data (Hospitalization on the same date = Yes/No) will be provided by OPTUM to enable the assessment of misclassification of the hospitalization.

All data analysis will be executed using statistical software SAS version 9.4 or later.

Detailed methodology for statistical analyses in this study will be documented in a statistical analysis plan (SAP), which will be dated, filed, and maintained. The SAP may modify the plans outlined in the protocol; any major modifications of primary endpoint definitions or their analyses would be reflected in a protocol amendment.

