9.2.1. Study Population and Cohorts

The study population will consist of patients who tested positive or were diagnosed for COVID-19 (ie, positive PCR or antigen results of direct SARS-CoV-2 viral testing or have confirmed COVID-19 diagnosis codes). All Paxlovid users will be included in the study.

Within the study population, three source cohorts of general population with COVID-19 will be formed (Figure 1):

- 1a: Overall COVID-19 patients.
- 1b: Hospitalized patients (ie, hospitalized within 30 days of index date) for COVID-19
- 1c: Non-hospitalized patients (ie, not hospitalized within 30 days of index date) with COVID-19

Within source cohort of 1a, 1b, and 1c, the following trial similar subcohorts, will be formed:

Patients at high risk of progression to severe illness (Figure 1)

- 2a: Subgroup of the general population cohort 1a who meet relevant inclusion/exclusion criteria of the Paxlovid clinical trial (C4671005).
- 2b: Subgroup of the hospitalized patient cohort 1b who meet relevant inclusion/exclusion criteria of the Paxlovid clinical trial (C4671005).
- 2c: Subgroup of the non-hospitalized patient cohort 1c who meet relevant inclusion/exclusion criteria of the Paxlovid clinical trial (C4671005).

Patients at standard risk of progression to severe illness Figure 1)

- 3a: Subgroup of the general population cohort 1a who meet relevant inclusion/exclusion criteria of the Paxlovid clinical trial (C4671002).
- 3b: Subgroup of the hospitalized patient cohort 1b who meet relevant inclusion/exclusion criteria of the Paxlovid clinical trial (C4671002).

[figure not shown]
 3c: Subgroup of the non-hospitalized patient cohort 1c who meet relevant inclusion/exclusion criteria of the Paxlovid clinical trial (C4671002).

A sub-cohort of patients who were exposed to Paxlovid in real world settings will be created.

If a patient had an exposure to paxlovid without COVID PCR/antigen testing/diagnosis data, this patient can be captured in the Paxlovid cohort.

Additional special populations (eg, immunocompromised patients, pediatric population, severe renal impairment, etc.) may be added as a subset.

A validation substudy will be a subpopulation randomly drawn from within the OPTUM EHR database. Figure 1. Flowchart Outlining the Study Cohort and Subcohorts

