9.2.2.4. Follow-up

The follow-up period starts at index date and participants will be followed until the date of the first occurring of the following events:

- Death;
- At the end of their database disenrollment from the database;
- At the end of study period (Section 9.2.2.1);
- Occurrence of the outcome of interest.

Follow-up time for hospitalized patients will meet the criterion in Section 9.2.1 (ie, hospitalized within 30 days of COVID 19 diagnosis or index date). Details as well as follow-up windows for long COVID will be defined in SAP.

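### Cumulative incidence of non-fatal endpoints is to be read from 1-Kaplan-Meier with death censored, which overstates it wherever patients die event-free before later events

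*Protocol*

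**What the plan says.** Section 9.9 (Data Analysis) plans a crude cumulative incidence and an incidence rate for each dichotomous endpoint, which "will be estimated for the Source Cohort and the Trial Similar Subcohorts". It names the estimator of the former: "Cumulative incidence and its 95% confidence interval (CI) will be estimated and illustrated using 1-Kaplan-Meier curves". It also sets the end of follow-up, which "will end on the first occurrence of an endpoint, disenrollment, study end date, or death, whichever comes first". Section 9.2.2.4 has the same rule: "The follow-up period starts at index date and participants will be followed until the date of the first occurring of the following events", and death heads the list that follows.

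Section 9.9 then adds: "Different endpoints will not censor each other's follow-up". All-cause mortality is itself an endpoint in Section 9.4, so this sentence does not sit well with the rule that death ends follow-up.

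The endpoints in Section 9.4 include many non-fatal ones: pneumonia, kidney failure, thrombotic events, ARDS, ventilation or ECMO, and the long COVID conditions. In-hospital death is listed as well. Section 9.9 leaves the handling of prevalent cases and the subpopulation analyses to the SAP, and Sections 9.2.2.4 and 9.4 leave the long COVID windows to it. The estimator is not deferred.

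**The concern.** Kaplan-Meier assumes that a censored patient keeps the same future risk of the event as those still under observation. That can be defended for disenrollment or study end. It cannot hold for death, because a patient who has died can no longer develop ARDS or long COVID. With deaths censored, 1-Kaplan-Meier describes a hypothetical population in which nobody dies, not the proportion of patients who actually experience the event. In-hospital death has the same difficulty, because a patient who dies outside hospital can no longer die in it.

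Background incidence is what primary Objectives 3 and 4 are meant to deliver, and Section 7 wants it as context for safety events seen with Paxlovid. A background figure that is too high makes an observed frequency look less unusual than it is. The error depends on mortality, so it need not be the same size in each cohort. Confidence intervals from a large database would not reveal it.

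**Working it through.** **Inputs.** The estimator, the end-of-follow-up rule and the endpoint list come from Protocol Sections 9.9, 9.2.2.4 and 9.4. The protocol gives no mortality, event risk or target precision, so there is no figure of its own to reproduce. All rates below are assumptions.

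**Formulas, constant hazards over one window.** Let K be the reported 1-Kaplan-Meier value. Let d be the net death risk, meaning the risk implied by the death hazard among patients still free of the endpoint.

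- Event hazard: λ1 = −ln(1 − K)
- Death hazard: λ2 = −ln(1 − d)
- Cumulative incidence: CIF = λ1/(λ1 + λ2) × [1 − (1 − K)(1 − d)]

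**K = 20%, so λ1 = 0.2231.**

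| d | λ2 | λ1/(λ1+λ2) | 1 − (1−K)(1−d) | CIF | K/CIF |
|---|---|---|---|---|---|
| 2% | 0.0202 | 0.917 | 0.216 | 19.8% | 1.01 |
| 10% | 0.1054 | 0.679 | 0.280 | 19.0% | 1.05 |
| 20% | 0.2231 | 0.500 | 0.360 | 18.0% | 1.11 |
| 30% | 0.3567 | 0.385 | 0.440 | 16.9% | 1.18 |

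**Low mortality.** With K = 30% and d = 1%, the CIF is 29.86%, a difference of 0.14 percentage points.

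**Simulation check.** With 400,000 patients, K = 30% and d = 15%, 1-Kaplan-Meier came to 30.1%. The proportion who actually had the event was 27.9%, and the formula gives 27.8%.

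**Effect of timing.**

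- Early events: with the event hazard decaying with a time constant of 3 days over a 30-day window, K = 30% and d = 15%, the CIF is 29.6% (ratio 1.015). Most events occur before deaths can compete.
- Late events: suppose follow-up runs from index, events can count only after day 30, and all deaths fall before that. Then CIF = (1 − d) × K. With K = 30% this is 0.98 × 30% = 29.4% at 2% early death, 0.85 × 30% = 25.5% at 15% (ratio 1.18) and 0.80 × 30% = 24.0% at 20% (ratio 1.25).

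**Outputs that are not affected.**

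- All-cause mortality: nothing competes with it.
- Thirty-day hospitalization in cohorts 1b and 1c: it is 100% and 0% by the cohort definitions in Section 9.2.1, whichever estimator is used.
- Incidence rates: events over person-time, with follow-up stopped at death, are valid cause-specific rates.

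**The case against.** Several points on the other side stand.

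- A reader might infer that every non-fatal endpoint is overestimated. The documents do not support that: 30-day hospitalization in 1b and 1c is fixed by definition, and events close to the index date are barely touched.
- A reader might infer that the hospitalized cohorts are shown to be the worst affected. Higher mortality there is plausible, but the protocol gives none for any cohort. Total hospital mortality would also be the wrong number to put into the table. Only deaths in patients still free of the endpoint compete; a death after ARDS or ventilation adds nothing to the bias for that endpoint.
- A reader might infer that comparisons between cohorts are invalidated. Section 9.7 calls the study descriptive and puts comparative analyses outside its scope, and Section 9.9 plans no formal contrast between hospitalized and non-hospitalized patients.
- The larger ratios for long COVID depend on windows that the protocol leaves to the SAP. If the risk set starts with patients alive when the window opens, that part of the bias goes.
- The incidence rates are reported alongside and can serve the research question on background rates.
- Ending follow-up at death is not itself an error. It does so under a competing-risk analysis too.

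Two further defences do not succeed. Section 9.9 allows the SAP to modify the plan, but the protocol states an estimator, so the text is wrong as it stands rather than merely silent. The sentence that endpoints do not censor each other might be read as keeping deceased patients in the risk set, but the rule that names death explicitly as an end of follow-up contradicts that reading.

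**Conclusion.** The point holds in bounded form. As written, Section 9.9 yields a cumulative incidence at or above the true one for non-fatal endpoints and for in-hospital death, and above it whenever competing deaths precede later events. Under constant hazards, the relative overstatement at a reported 20% runs from about 1% at 2% net death risk to about 18% at 30%. These are illustrations, not estimates for this database. The bias is negligible at low mortality or for early events. It would be larger in cohorts with higher mortality, plausibly the hospitalized ones, and for late endpoints counted from index.

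This should be fixed, because the estimator is stated, its error has a known direction, and it bears on primary objectives. It does not invalidate the study: no hypothesis, decision threshold or treatment comparison rests on these curves, and the cause-specific rates remain sound.

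**What to change.** In Section 9.9:

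1. Replace 1-Kaplan-Meier by the Aalen-Johansen cumulative incidence function, with its own 95% confidence interval, for all non-fatal endpoints, with death as a competing event.
2. For in-hospital death, treat out-of-hospital death as the competing event.
3. Keep 1-Kaplan-Meier for all-cause mortality.
4. Keep the incidence rates and label them cause-specific.
5. State that the rule that endpoints do not censor each other does not apply to death, which ends follow-up for every endpoint.

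The cost is a few sentences in the protocol, carried into the SAP, and a change of estimator in the programs. Mortality is already among the data elements in Section 9.6, so no new data are needed. The affected incidences will come out the same or somewhat lower.

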9.2. Setting

This study will be conducted using Optum's COVID-19 Electronic Health Record Data during the period of January 01, 2020, to June 30, 2024. Details about the database are found in Section 9.6. The COVID-era cohorts will be refreshed annually to include additional individuals, follow-up time, and events. These refreshes and cohorts will accordingly be described in a Statistical Analysis Plan (SAP) or protocol amendment as appropriate.

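### Complications are limited to 30 days, but the follow-up rule has no stop at the end of that window, so their incidence rates as written divide 30-day events by longer person-time

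*Protocol*

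**What the plan says.** Four statements in the protocol bear on the point.

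- **Endpoint definition (Section 9.4).** The list that includes pneumonia, kidney failure, thrombotic events, ARDS, sepsis and others is headed "COVID-19 complications/interventions (within 30 days of COVID 19 diagnosis").
- **What is estimated (Section 9.9).** In the Source Cohort and the Trial Similar Subcohorts, the plan is this: "For dichotomous endpoints such as COVID-19 complications and outcomes, the crude cumulative incidence and incidence rate of each endpoint will be estimated".
- **How the rate is built (Section 9.9).** For the numerator, "only the first of each event occurring in the risk window will be included in the numerator". For the whole rate: "Incidence rate will be calculated as the number of patients who experience the event divided by the total person time at risk".
- **When follow-up ends (Sections 9.9 and 9.2.2.4).** Section 9.9 says: "The follow-up will start on the index date and will end on the first occurrence of an endpoint, disenrollment, study end date, or death". Section 9.2.2.4 gives the same four stops, including "At the end of study period (Section 9.2.2.1").

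Neither follow-up passage mentions day 30 or the end of a risk window. On what is left for later, Section 9.2.2.4 says: "Details as well as follow-up windows for long COVID will be defined in SAP".

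**The concern.** For the Source Cohort and the Trial Similar Subcohorts the index date is the first positive test or diagnosis (Section 9.2.2.3). The 30-day window and the follow-up clock therefore start together, and only their ends differ. A patient with no complication by day 30 can no longer enter the numerator, yet under the written rule still adds person-time until disenrollment, death or study end. Avoiding this by counting later events would break the 30-day definition in Section 9.4.

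Background incidence of COVID-19 complications is Primary Objective 3 (Section 8), and Section 7 presents such information as context for interpreting events in trials and after marketing. A rate whose size depends on follow-up length does not serve that purpose. Results are stratified by calendar period (Section 9.2.2.1) and the cohorts are refreshed annually with added follow-up time and added patients (Section 9.2). Follow-up will therefore differ between the sets of results that readers will put side by side.

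**Working it through.** The protocol states no rate, event risk or sample size target, so there is no figure of its own to reproduce. The check has two parts.

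**1. Do the two ends match?**

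| Element | Section | Ends at |
|---|---|---|
| Complication counts as an event | 9.4 | day 30 after diagnosis |
| Event enters the numerator | 9.9 | end of a risk window, undefined |
| Follow-up | 9.9 and 9.2.2.4 | outcome, disenrollment, study end or death |

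The numerator closes at day 30. The follow-up from which person-time is built does not.

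**2. How large could the effect be?**

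Inputs:
- Window of 30 days: Section 9.4.
- Longest possible follow-up: Section 9.2 sets the study "during the period of January 01, 2020, to June 30, 2024", which spans 1,642 days.
- 30-day risk *p* and follow-up length *F*: not given in the protocol, so assumed. The ranges are *p* from 1% to 20% and *F* from 90 to 1,642 days.
- Simplifications: constant hazard over the 30 days, and every event-free patient followed to day *F*.

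Formulas:
- Daily hazard: λ = −ln(1 − p) / 30
- Mean person-days to day 30: PT30 = p / λ
- Mean person-days when follow-up runs to day F: PT(F) = PT30 + (1 − p)(F − 30)
- Rate per 100 person-years = p / PT × 36,525
- Dilution factor = PT(F) / PT30, because the numerator is the same

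With p = 10%: λ = 0.10536 / 30 = 0.003512 per day, and PT30 = 0.1 / 0.003512 = 28.5 days.

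| Person-time ends at | Mean person-days | Rate per 100 person-years | Dilution |
|---|---|---|---|
| day 30 | 28.5 | 128.3 | none |
| day 180 | 28.5 + 0.9 × 150 = 163.5 | 22.3 | 5.7-fold |
| day 365 | 28.5 + 0.9 × 335 = 330.0 | 11.1 | 11.6-fold |
| day 730 | 28.5 + 0.9 × 700 = 658.5 | 5.5 | 23.1-fold |
| day 1,642 | 28.5 + 0.9 × 1,612 = 1,479.3 | 2.5 | 52.0-fold |

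The dilution depends mainly on follow-up length and little on the assumed risk:

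| Follow-up | p = 1% | p = 5% | p = 10% | p = 20% |
|---|---|---|---|---|
| 90 days | 3.0 | 2.9 | 2.9 | 2.8 |
| 365 days | 12.1 | 11.9 | 11.6 | 11.0 |
| 1,642 days | 54.5 | 53.4 | 52.0 | 49.0 |

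Comparability: two groups with the same 10% 30-day risk, one followed for 730 days and the other for 180, would show 5.5 and 22.3 per 100 person-years. That is a four-fold difference (22.3 / 5.5) produced by follow-up alone.

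With person-time stopped at day 30, the rates for risks of 1%, 5%, 10% and 20% are 12.2, 62.4, 128.3 and 271.7 per 100 person-years, whatever the later follow-up.

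**The case against.** The strongest counter-reading is that the denominator is person-time *at risk* and the numerator is tied to a risk window. In ordinary epidemiological usage, time after the window closes is not time at risk. The follow-up sentence would then be only an outer limit, needed because the same paragraph serves endpoints with different windows. This is plausible, and it may be what the authors intend. It does not settle the matter. The risk window is never defined, and the follow-up rule in Section 9.9 fixes the end of follow-up without mentioning it, as does Section 9.2.2.4. Two programmers working from this text could produce different denominators.

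A second objection is that the SAP, not shown here, may supply the stop. It may: Section 9.2.2.4 leaves unspecified details to it, and Section 9.9 lets it modify the protocol's plans. But the only follow-up windows expressly deferred are those for long COVID, and the point concerns a rule the protocol states twice, not a detail it leaves open.

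Some stronger conclusions are tempting but not supported:

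- **All incidence results are wrong.** The 1-Kaplan-Meier estimate, planned for the same endpoints, is not diluted when read at day 30.
- **Comparisons with adverse event rates in trials are distorted.** The 30-day limit heads only the complications list. The potential safety outcomes in Section 9.4 have no such limit, so this mismatch does not arise for them. Whether they should have event-specific windows is a separate question.
- **The pre-vaccine period must look safer than the Paxlovid period.** This assumes patients are followed beyond the sub-period in which they entered. If the end of study period means the end of the sub-period, follow-up in the first one is at most about ten months and the direction could reverse.
- **The rate must fall at every refresh.** Refreshes also add new patients with short follow-up, so mean follow-up need not rise.
- **The understatement is an order of magnitude.** That holds at about one year of follow-up. It is about three-fold at 90 days and larger with longer follow-up, and in every case only if the follow-up rule is applied literally.

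**Conclusion.** The concern holds for the incidence rates of the 30-day complications in Section 9.4. The definition closes the numerator at day 30, and neither statement of the follow-up rule closes the person-time there. Applied as written, the rate is too low by a factor set mainly by follow-up length: for an assumed 10% risk, 5.7-fold at 180 days, 11.6-fold at 365 days and 23-fold at 730 days. Rates from cohorts or refreshes with different follow-up would not be comparable, although the direction of any particular difference cannot be predicted from the protocol.

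The multiples rest on assumed risks and follow-up, a constant hazard within the window, and the literal reading of the follow-up rule. On the more generous reading of time at risk there is no dilution, but the protocol still leaves a needed term undefined and lists stops that omit it. Because a primary objective depends on these rates, the text should be settled before they are produced.

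**What to change.** In Sections 9.2.2.4 and 9.9, add to the follow-up stops for the incidence-rate calculation: end of the endpoint's risk window (day 30 for the complications listed in Section 9.4). Numerator and person-time are then truncated on the same day. Define the risk window for each endpoint to which one applies, in the protocol or by explicit reference to the SAP.

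The cost is one bullet in Section 9.2.2.4, one clause in Section 9.9 and one extra censoring date in the programs. No new data are needed, and the Kaplan-Meier analysis need not change.
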